17.3. ECG EVALUATIONS

The 12-Lead Electrocardiogram (ECG) will be performed at screening, and on Days 1 and 15 in Cycle 1, when ECG data will be collected at pre-dose and at 2 hours +15 minutes post-dose (around C_{max} after single dose and at steady state in order to evaluate concentration-QT relationship for surufatinib). The ECG values at C1D1 pre-dose will be used as 'baseline' value in the analysis. ECG will also be conducted on Day 1 of each cycle from Cycle 2 and onward, as well as the treatment completion visit.

For each time-point, following measurements with change from baseline values will be presented for the SAS:

- Heart rate (bpm)
- RR (ms)
- PR (ms)
- QRS (ms)
- QT (ms)
- QT correction by Bazett (ms)
- QT correction by Fridericia (ms)
- Overall ECG interpretation
 - Abnormal, clinically significant (CS)
 - Abnormal, not clinically significant (NCS)
 - Normal
 - Incomplete analysis
 - Uninterpretable
 - Not applicable

17.3.1. ECG Specific Derivations

There will be no specific derivations for ECG.

[figure not shown]
17.3.2. ECG Markedly Abnormal Criteria

The number and percentage of patients with notable ECG values at baseline and post-baseline will be summarized. These summaries will be done for worst post-baseline value for each category. The criteria for notable ECG values are provided in Table 2 below.

Table 2 **Notable ECG Values**

Test	Notable ECG Values
------	--------------------

CCI

QTcF/QTcB (absolute)	interval >450 to 480 msec interval >480 to 500 msec interval >500 msec
Heart rate (absolute)	<50 bpm >100 bpm
PR (absolute)	interval >200 msec
QRS (absolute)	interval >120 msec

•

17.3.3. Analysis of QTc Change from Baseline (Δ QTc)

The change from baseline in QTcF (Δ QTcF) intervals will be evaluated as follows:

- Δ QTcF at each time point will be listed for each patient and treatment. For each time point of measurement, Δ QTcF will be summarized using descriptive statistics (mean, SD, median, min, max).
- The incidence of patients with Δ QTcF increase >30 to 60 msec and >60 msec will be summarized.
- The incidence of patients with Δ QTcF increase >30 to 60 msec and >60 msec by time-point in Cycle 1 will also be summarized.
- Patients with Δ QTcF increase >60 msec will be listed.
- Mean Δ QTcF versus time profile for each dose group will be plotted on the same graph.

17.3.4. Analysis of the Relationship Between QT/QTc and RR at Baseline

The relationship between QT/QTc and RR intervals at baseline will be evaluated graphically as follows:

- The logarithm of baseline QT values will be plotted against the logarithm of corresponding RR intervals.
- A linear regression model will be fitted to the data with logarithm of baseline QTc interval values as the dependent variable and logarithm of RR as the predictor.
- The slope of the regression line and its standard error, along with 2-sided 95% confidence intervals for the slope, will be estimated from this model.
- The analysis will be repeated for QTcB and QTcF and plotted on the same graph for QT.

CCI

17.4. VITAL SIGNS

The following Vital Signs measurements will be reported for this study:

- Systolic blood pressure (mmHg)
- Diastolic blood pressure (mmHg)
- Heart rate (beats/min)
- Respiratory Rate (breaths/min)
- Temperature (°C)
- Weight (kg)
- Baseline BMI (kg/m²)
- Baseline Height (cm)

Vital sign values and change from baseline (applicable to post-baseline measurements) will be summarized by each scheduled time-point.

All vital signs results including change from baseline for quantitative parameters will be listed. A flag of oral temperature derived from axillary temperature will be provided.

Selected vital signs (SBP, DBP and heart rate) change from baseline will be plotted over time for each patient.

17.4.1. Vital Signs Specific Derivations

There will be no specific derivations for vital signs.

17.4.2. Vital Signs Markedly Abnormal Criteria

Markedly abnormal quantitative Vital Signs measurements will be identified in accordance with the following predefined markedly abnormal criteria:

Table 3 **Vital Sign Markedly Abnormal Criteria.**

Variable	Unit	Baseline Category	High
SBP	mmHg	≤ 140 mmHg	Absolute change from baseline of: > 0 - ≤ 20 / > 20 - ≤ 40 / > 40 mmHg
DBP	mmHg	≤ 90 mmHg	Absolute change from baseline of: > 0 - ≤ 20 / > 20 - ≤ 40 / > 40 mmHg

Variable	Unit	Baseline Category	High
Heart rate	Bpm	< 100 / \geq 100 bpm	Absolute change from baseline of: $> 0 - \leq 20$ / $> 20 - \leq 40$ / > 40 bpm
Weight	Kg	None	Percentage change from baseline of $< 5\%$ / $\geq 5 - < 10\%$ / $\geq 10 - < 20\%$ / $\geq 20\%$

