7.2.3 Dose Modification for Important Identified Risks

Dose modifications for important identified risks are provided in Table 7 (hypertension), [Table 8](#) (proteinuria), [Table 9](#) (liver function impairment), and [Table 10](#) (hemorrhage).

Table 7 Dose Modification for Hypertension

Grade and Definition	Dose Modification	Suggested Actions
Grade 1: prehypertension (systolic BP120-139 mmHg or diastolic BP 80-89 mmHg)	None.	None.
Grade 2: Stage 1 hypertension (systolic BP140-159 mmHg or diastolic BP 90-99 mmHg); medical intervention indicated; recurrent or persistent(≥24 hours); symptomatic increase by >20 mmHg (diastolic) or to >140/90 mmHg if previously within normal range; monotherapy indicated	None.	Treatment target: control blood pressure to below 140/90 mmHg. If patient has already received antihypertensive treatment at baseline, the dose should be increased or treatment changed. If patient did not receive treatment at baseline, monotherapy should be administered. Refer to relevant anti-hypertensive treatment guidelines for dose administration and modification and consult cardiologist if necessary.
Grade 3: Stage 2 hypertension (Systolic pressure ≥ 160mmHg or diastolic pressure ≥ 100mmHg); medical intervention indicated; more than one drug or more intensive therapy than previously used indicated	If BP >160/100mmHg lasts for >3 days after initiation of anti-hypertensive treatment or modification of current anti-hypertensive treatment, surufatinib treatment should be held. If hypertension resolves to Grade 1 or baseline level within 21 days, sulfatinib treatment could be re-started at a lower dose level.	Treatment target: control blood pressure below 140/90 mmHg. Initiate antihypertensive treatment, increase dose of current treatment, or add other treatments. For use and adjustment of antihypertensive treatment, refer to relevant treatment guidelines or consult cardiologist if necessary.

Table 7 Dose Modification for Hypertension

Grade and Definition	Dose Modification	Suggested Actions
Grade 4: Life-threatening consequences (e.g., malignant hypertension, transient or permanent neurologic deficit, hypertensive crisis); urgent intervention indicated	Discontinue surufatinib treatment.	Emergent medical intervention.

Table 8 Dose Modification for Proteinuria

Grade and Definition	Dose Modification	Suggested Actions
Grade 1: 1+ proteinuria; urinary protein <1.0 g/24 hours	None.	Follow up as planned schedule.

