7.7. COMMON CALCULATIONS

For quantitative measurements, change from Baseline will be calculated as:

- Change from baseline = Test Value at Visit X – Baseline Value
- Percentage change from baseline = $[(\text{Test Value at Visit X} - \text{Baseline Value}) / \text{Baseline Value}] * 100$

The time from Date of Event A to Date of Event B (years) is calculated as:

- $(\text{Date of Event B} - \text{Date of Event A} + 1) / 365.25$.

The time from Date of Event A to Date of Event B (months) is calculated as:

- $(\text{Date of Event B} - \text{Date of Event A} + 1) / 30.4375$.

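### SAP Table 3 does not give a direction for its weight categories, so the markedly abnormal table cannot show weight loss as such

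*SAP*

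**What the plan says.** SAP section 17.4.2 introduces Table 3 as a rule: "Markedly abnormal quantitative Vital Signs measurements will be identified in accordance with the following predefined markedly abnormal criteria". The table has one result column, High, and no Low column.

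- **Weight** has no baseline category and is divided as "Percentage change from baseline of $< 5\%$ / $\geq 5 - < 10\%$ / $\geq 10 - < 20\%$ / $\geq 20"%. The first category has no lower bound, and nothing in the row mentions gain or loss.
- **SBP and DBP** are divided as "Absolute change from baseline of: > 0 - ≤ 20 / > 20 - ≤ 40 / > 40 mmHg", for baseline ≤140 mmHg and ≤90 mmHg respectively.
- **Heart rate** uses the same cut-points in bpm, but has both baseline categories (<100 and ≥100 bpm).

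Section 7.7 sets the general formulas under "For quantitative measurements, change from Baseline will be calculated as": test value minus baseline for change, and that difference divided by baseline, times 100, for percentage change. Both keep the sign. Section 17.4.1 states that vital signs have no specific derivations, so nothing overrides section 7.7.

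**The concern.** A categorical table of marked changes should let a reader count patients with a large change in the direction of interest. Vital signs are a stated secondary safety endpoint (Protocol 4.2.4), and diarrhea is among the treatment-related events reported in at least 20% of patients (Protocol 2.3). A count of patients with 5%, 10% or 20% weight loss would therefore be useful in the report.

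Table 3 does not deliver that count on either reading. The silence on direction also means that two programmers could produce different tables from the same data. Elsewhere the SAP handles direction explicitly: ECG heart rate has a low and a high limit (17.3.2), laboratory values are low, normal or high (17.2.2), and CTCAE laboratory grades are split into hyper and hypo (17.2.3).

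**Working it through.** The plan gives no figure to reproduce here, so the check applies its own formula to its own categories.

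**Inputs.** Percentage change = (test − baseline) / baseline × 100 (SAP 7.7). Weight categories from Table 3. The baseline weight of 80 kg is illustrative; only the percentage matters.

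**Weight**

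| Post-baseline weight | Percentage change | Category, signed (SAP 7.7) | Category, unsigned |
|---|---|---|---|
| 48 kg | (48 − 80)/80 × 100 = −40 | <5% | ≥20% |
| 64 kg | −20 | <5% | ≥20% |
| 68 kg | −15 | <5% | ≥10 to <20% |
| 72 kg | −10 | <5% | ≥10 to <20% |
| 76 kg | −5 | <5% | ≥5 to <10% |
| 80 kg | 0 | <5% | <5% |
| 84 kg | +5 | ≥5 to <10% | ≥5 to <10% |
| 88 kg | +10 | ≥10 to <20% | ≥10 to <20% |
| 96 kg | +20 | ≥20% | ≥20% |

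With the sign kept, all losses share a category with no change. With the sign dropped, 72 kg and 88 kg share a category, as do 64 kg and 96 kg.

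**Blood pressure and heart rate.** With signed change, falls of 10, 30 or 50 units land in no category, which is consistent with a column headed High. With magnitude, the same falls would land in the >0 to ≤20, >20 to ≤40 and >40 categories and be reported as high. The word 'absolute' in these rows could mean either magnitude or the opposite of percentage. The High heading and the contrast with the percentage wording of the weight row favour the second meaning, but the SAP does not say so.

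**Baseline rows**

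| Baseline BP (mmHg) | SBP row? | DBP row? | Meets exclusion criterion 8 (SBP ≥140 and/or DBP ≥90)? |
|---|---|---|---|
| 138/88 | yes | yes | no |
| 141/88 | no | yes | yes |
| 150/95 | no | no | yes |

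Any baseline that falls outside a row also meets the exclusion criterion. Such a patient can be in the data only through a deviation, or because the analysis baseline is the last pre-dose value, unscheduled readings included (SAP 7.2), while screening may take place up to 28 days before the first dose (Protocol 8.3.1).

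**The case against.** The strongest reply is that the direction is merely unstated and may be settled elsewhere. SAP section 9 says that the templates supplied with the SAP fix the format and content of the tables, and those templates are not in the text reviewed. This stands as a limit on certainty. It does not remove the need for the rule itself to give a direction, since section 17.4.2 presents it as predefined. A column lost when the PDF was read also cannot be fully excluded, although the table header appears twice with only High.

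Several stronger inferences are tempting, and the documents do not support them:

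- *Weight loss goes unreported.* It does not. Section 17.4 summarizes values and changes at each scheduled time-point and lists all results, and section 9 includes the minimum and maximum, so the largest loss at each visit is visible. The cover is partial: unscheduled values are left out of by-visit summaries (7.4), and the per-patient plots cover SBP, DBP and heart rate but not weight.
- *Every 1 mmHg rise is declared markedly abnormal.* The lowest tier reads more naturally as a display category beside the higher ones. On the same literal reading, an unchanged weight would be markedly abnormal too.
- *Patients with high baseline pressure are dropped on any scale.* Exclusion criterion 8 explains the single baseline rows and should make such cases few. The gap also applies per parameter, as the 141/88 example shows.
- *Hypertension severity is lost because Table 3 ignores the level reached.* TEAEs are summarized by CTCAE grade (17.1.1.1), Protocol Table 7 describes the hypertension grades by blood pressure level, and hypertension has its own special-interest summary with time to onset (17.1.5). Counts by measured level would add information but would not correct an error.

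**Conclusion.** The point holds for the weight row. Under the formula in SAP 7.7, every weight loss, whatever its size, falls in the lowest category of Table 3. Under an unsigned reading, losses are counted but mixed with gains. The signed reading has the better textual support, but the conclusion that the table does not show weight loss as such does not depend on choosing between them. It assumes only that the table templates do not already split the row.

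The size is modest. One categorical safety table is affected. No primary endpoint or data collection is touched, and weight loss is not among the identified or potential risks listed in Protocol 3.3. The missing SBP and DBP baseline categories are a minor gap. The documents give no frequency for them, and criterion 8 implies that few patients are concerned.

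**What to change.** In SAP Table 3:

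1. Replace the weight row with two rows, decrease and increase, each with categories ≥5 to <10%, ≥10 to <20% and ≥20%. Use the worst post-baseline value in each direction, so that a patient may count once in each row. Section 7.4 already lets unscheduled values contribute to worst-case summaries.
2. State that the SBP, DBP and heart rate categories are increases from baseline.
3. Minor: add baseline categories SBP >140 and DBP >90 mmHg, so that a patient whose last pre-dose reading exceeds a limit is not left out of that parameter's summary.

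Optional: tabulate worst post-baseline SBP and DBP by the levels already used in Protocol Table 7 (140/90 and 160/100 mmHg) next to the change categories.

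The cost is a SAP text edit, a matching check of the table templates and minor programming. All the data are already collected.

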17.5. PHYSICAL EXAMINATION

A complete physical examination at screening should include the evaluation of head, eye, ear, nose, and throat; and cardiovascular, dermatological, musculoskeletal, respiratory, gastrointestinal, and neurological systems.

At subsequent visits, a limited physical examination will be performed to assess changes from baseline abnormalities, any new abnormalities, and to evaluate patient-reported symptoms. New or worsened abnormalities should be recorded as AEs if appropriate.

All physical examination results will be listed.

17.6. OTHER SAFETY ASSESSMENTS

17.6.1. ECOG Performance Status

The Eastern Cooperative Oncology Group (ECOG) Performance Status will be summarized descriptively by visit and a shift table will be also summarized from the “ECOG Performance Status” CRF page. In addition, the summary descriptive table by visit will include specific ECOG grades and binary grouping grades (0-1, 2-5). The shift table will be summarized from baseline to worst post-baseline.

Details about ECOG performance status scores can be found in Protocol Appendix B.

[figure not shown]
A listing of ECOG Performance Status will be provided.

17.6.2. Echocardiogram

Echocardiography, including left ventricular ejection fraction (LVEF) assessment contains both quantitative results (%) and overall evaluation [Normal; Abnormal, Not Clinically Significant (ANCS); Abnormal, Clinically Significant (ACS)].

Actual value of echocardiography measured at each scheduled visit, change from baseline to each post-baseline

CCI

scheduled measurement will be presented by visit. Overall evaluation will be summarized separately.

All echocardiography results including change from baseline for LVEF and relevant information will be listed.

APPENDIX 1. PROGRAMMING CONVENTIONS FOR OUTPUTS

IQVIA OUTPUT CONVENTIONS

Outputs will be presented according to the Quintiles' general guidelines and template for outputs conventions.

DATES & TIMES

Depending on data available, dates and times will take the form DDMMYY and HH:MM:SS.

SPELLING FORMAT

English US.

PRESENTATION OF TREATMENT GROUPS

All summaries will be presented by assigned dose level in dose escalation phase.

Treatment Group	For Tables, Listings and Graphs
50 mg/day dose level	50 mg
100 mg/day dose level	100 mg
200 mg/day dose level	200 mg
300 mg/day dose level	300 mg
400 mg/day dose level	400 mg
Additional intermediate dose level	XXX mg (XXX=Actual dose level)
Screen failures (in listings only)	SF
Untreated eligible patients (in listings only)	NOTRT

CCI

PRESENTATION OF DISEASE COHORT

All summaries will be presented by disease cohort in dose expansion phase.

Disease Cohort	For Tables, Listings and Graphs
Arm A: Biliary tract cancer	BTC
Arm B: Pancreatic neuroendocrine tumor	pNET
Arm C: Extrapancreatic neuroendocrine tumor	epNET
Arm D: Soft tissue sarcoma	STS

PRESENTING ORDER

All listings will be ordered by the following (unless otherwise indicated in the template):

[figure not shown]
- SitePatient ID,
- Treatment group, in the order as above table,
- date (where applicable)

All tables containing coded terms (CM, MH, AE, etc), coded records will be sorted in descending order of incidence.

APPENDIX 2. ADVERSE EVENTS OF SPECIAL INTEREST

AESI SMQ	PT Term	PT Code
Acute renal failure	Acute kidney injury	10069339
	Acute phosphate nephropathy	10069688
	Anuria	10002847
	Azotaemia	10003885
	Continuous haemodiafiltration	10066338
	Dialysis	10061105
	Foetal renal impairment	10078987
	Haemodialysis	10018875
	Haemofiltration	10053090

CCI

	Neonatal anuria	10049778
	Nephropathy toxic	10029155
	Oliguria	10030302
	Peritoneal dialysis	10034660
	Prerenal failure	10072370
	Renal failure	10038435
	Renal failure neonatal	10038447
	Renal impairment	10062237
	Renal impairment neonatal	10049776
	Subacute kidney injury	10081980
Haemorrhages	Abdominal wall haematoma	10067383
	Abdominal wall haemorrhage	10067788
	Abnormal withdrawal bleeding	10069195
	Achenbach syndrome	10079562
	Acute haemorrhagic leukoencephalitis	10058994
	Acute haemorrhagic ulcerative colitis	10075634
	Administration site bruise	10075094
	Administration site haematoma	10075100
	Administration site haemorrhage	10075101
	Adrenal haematoma	10059194
	Adrenal haemorrhage	10001361
	Anal fissure haemorrhage	10079765
	Anal haemorrhage	10049555
	Anal ulcer haemorrhage	10063896
	Anastomotic haemorrhage	10056346
	Anastomotic ulcer haemorrhage	10002244
	Aneurysm ruptured	10048380
	Angina bullosa haemorrhagica	10064223
	Anorectal varices haemorrhage	10068925
	Anticoagulant-related nephropathy	10083346
	Aortic aneurysm rupture	10002886
	Aortic dissection rupture	10068119
	Aortic intramural haematoma	10067975
	Aortic perforation	10075729
	Aortic rupture	10060874
	Aponeurosis contusion	10075330
	Application site bruise	10050114
	Application site haematoma	10068317
	Application site haemorrhage	10072694
	Application site purpura	10050182
	Arterial haemorrhage	10060964
	Arterial intramural haematoma	10074971
	Arterial perforation	10075732
	Arterial rupture	10003173
	Arteriovenous fistula site haematoma	10055150
	Arteriovenous fistula site haemorrhage	10055123
	Arteriovenous graft site haematoma	10055152

CCI

Arteriovenous graft site haemorrhage	10055126
Astringent therapy	10067372
Atrial rupture	10048761
Auricular haematoma	10003797
Basal ganglia haematoma	10077031
Basal ganglia haemorrhage	10067057
Basilar artery perforation	10075736
Bladder tamponade	10062656
Bleeding varicose vein	10005144
Blood blister	10005372
Blood loss anaemia	10082297
Blood urine	10005863
Blood urine present	10018870
Bloody discharge	10057687
Bloody peritoneal effluent	10067442
Bone contusion	10066251
Bone marrow haemorrhage	10073581
Brain contusion	10052346
Brain stem haematoma	10073230
Brain stem haemorrhage	10006145
Brain stem microhaemorrhage	10071205
Breast haematoma	10064753
Breast haemorrhage	10006254
Broad ligament haematoma	10006375
Bronchial haemorrhage	10065739
Bronchial varices haemorrhage	10079163
Bullous haemorrhagic dermatosis	10083809
Bursal haematoma	10077818
Cardiac contusion	10073356
Carotid aneurysm rupture	10051328
Carotid artery perforation	10075728
Catheter site bruise	10063587
Catheter site haematoma	10055662
Catheter site haemorrhage	10051099
Central nervous system haemorrhage	10072043
Cephalhaematoma	10008014
Cerebellar haematoma	10061038
Cerebellar haemorrhage	10008030
Cerebellar microhaemorrhage	10071206
Cerebral aneurysm perforation	10075394
Cerebral aneurysm ruptured syphilitic	10008076
Cerebral arteriovenous malformation haemorrhagic	10008086
Cerebral artery perforation	10075734
Cerebral cyst haemorrhage	10082099
Cerebral haematoma	10053942
Cerebral haemorrhage	10008111
Cerebral haemorrhage foetal	10050157

Cerebral haemorrhage neonatal	10008112
Cerebral microhaemorrhage	10067277
Cervix haematoma uterine	10050020
Cervix haemorrhage uterine	10050022
Chest wall haematoma	10076597
Choroidal haematoma	10068642
Choroidal haemorrhage	10008786
Chronic gastrointestinal bleeding	10050399
Chronic pigmented purpura	10072726
Ciliary body haemorrhage	10057417
Coital bleeding	10065019
Colonic haematoma	10009996
Conjunctival haemorrhage	10010719
Contusion	10050584
Corneal bleeding	10051558
Cullen's sign	10059029
Cystitis haemorrhagic	10011793
Deep dissecting haematoma	10074718
Diarrhoea haemorrhagic	10012741
Disseminated intravascular coagulation	10013442
Diverticulitis intestinal haemorrhagic	10013541
Diverticulum intestinal haemorrhagic	10013560
Duodenal ulcer haemorrhage	10013839
Duodenitis haemorrhagic	10013865
Dysfunctional uterine bleeding	10013908
Ear haemorrhage	10014009
Ecchymosis	10014080
Encephalitis haemorrhagic	10014589
Enterocolitis haemorrhagic	10014896
Epidural haemorrhage	10073681
Epistaxis	10015090
Exsanguination	10015719
Extra-axial haemorrhage	10078254
Extradural haematoma	10015769
Extradural haematoma evacuation	10082797
Extravasation blood	10015867
Eye contusion	10073354
Eye haematoma	10079891
Eye haemorrhage	10015926
Eyelid bleeding	10053196
Eyelid contusion	10075018
Eyelid haematoma	10064976
Femoral artery perforation	10075739
Femoral vein perforation	10075745
Foetal-maternal haemorrhage	10016871
Fothergill sign positive	10081749
Gastric haemorrhage	10017788

CCI

Gastric ulcer haemorrhage	10017826
Gastric ulcer haemorrhage, obstructive	10017829
Gastric varices haemorrhage	10057572
Gastritis alcoholic haemorrhagic	10017857
Gastritis haemorrhagic	10017866
Gastroduodenal haemorrhage	10053768
Gastrointestinal haemorrhage	10017955
Gastrointestinal polyp haemorrhage	10074437
Gastrointestinal ulcer haemorrhage	10056743
Gastrointestinal vascular malformation haemorrhagic	10080561
Genital confusion	10073355
Genital haemorrhage	10061178
Gingival bleeding	10018276
Graft haemorrhage	10063577
Grey Turner's sign	10075426
Haemangioma rupture	10084040
Haemarthrosis	10018829
Haematemesis	10018830
Haematochezia	10018836
Haematocoele	10018833
Haematoma	10018852
Haematoma evacuation	10060733
Haematoma infection	10051564
Haematoma muscle	10055890
Haematosalpinx	10050468
Haematospermia	10018866
Haematotympanum	10063013
Haematuria	10018867
Haematuria traumatic	10018871
Haemobilia	10058947
Haemoperitoneum	10018935
Haemophilic arthropathy	10065057
Haemophilic pseudotumour	10073770
Haemoptysis	10018964
Haemorrhage	10055798
Haemorrhage coronary artery	10055803
Haemorrhage foetal	10061191
Haemorrhage in pregnancy	10018981
Haemorrhage intracranial	10018985
Haemorrhage neonatal	10061993
Haemorrhage subcutaneous	10018999
Haemorrhage subepidermal	10019001
Haemorrhage urinary tract	10055847
Haemorrhagic adrenal infarction	10079902
Haemorrhagic arteriovenous malformation	10064595
Haemorrhagic ascites	10059766
Haemorrhagic breast cyst	10077443

Haemorrhagic cerebral infarction	10019005
Haemorrhagic cyst	10059189
Haemorrhagic diathesis	10062713
Haemorrhagic disease of newborn	10019008
Haemorrhagic disorder	10019009
Haemorrhagic erosive gastritis	10067786
Haemorrhagic hepatic cyst	10067796
Haemorrhagic infarction	10019013
Haemorrhagic necrotic pancreatitis	10076058
Haemorrhagic ovarian cyst	10060781
Haemorrhagic stroke	10019016
Haemorrhagic thyroid cyst	10072256
Haemorrhagic transformation stroke	10055677
Haemorrhagic tumour necrosis	10054096
Haemorrhagic urticaria	10059499
Haemorrhagic vasculitis	10071252
Haemorrhoidal haemorrhage	10054787
Haemostasis	10067439
Haemothorax	10019027
Henoch-Schonlein purpura	10019617
Hepatic haemangioma rupture	10054885
Hepatic haematoma	10019676
Hepatic haemorrhage	10019677
Hereditary haemorrhagic telangiectasia	10019883
Hyperfibrinolysis	10074737
Hyphaema	10020923
Iliac artery perforation	10075731
Iliac artery rupture	10072789
Iliac vein perforation	10075744
Immune thrombocytopenia	10083842
Implant site bruising	10063850
Implant site haematoma	10063780
Implant site haemorrhage	10053995
Incision site haematoma	10059241
Incision site haemorrhage	10051100
Increased tendency to bruise	10021688
Induced abortion haemorrhage	10052844
Inferior vena cava perforation	10075742
Infusion site bruising	10059203
Infusion site haematoma	10065463
Infusion site haemorrhage	10065464
Injection site bruising	10022052
Injection site haematoma	10022066
Injection site haemorrhage	10022067
Instillation site bruise	10073630
Instillation site haematoma	10073609
Instillation site haemorrhage	10073610

Internal haemorrhage	10075192
Intestinal haematoma	10069829
Intestinal haemorrhage	10059175
Intestinal varices haemorrhage	10078058
Intra-abdominal haematoma	10056457
Intra-abdominal haemorrhage	10061249
Intracerebral haematoma evacuation	10062025
Intracranial haematoma	10059491
Intracranial tumour haemorrhage	10022775
Intraocular haematoma	10071934
Intrapartum haemorrhage	10067703
Intraventricular haemorrhage	10022840
Intraventricular haemorrhage neonatal	10022841
Iris haemorrhage	10057418
Joint microhaemorrhage	10077666
Kidney contusion	10023413
Lacrimal haemorrhage	10069930
Large intestinal haemorrhage	10052534
Large intestinal ulcer haemorrhage	10061262
Laryngeal haematoma	10070885
Laryngeal haemorrhage	10065740
Lip haematoma	10066304
Lip haemorrhage	10049297
Liver contusion	10067266
Lower gastrointestinal haemorrhage	10050953
Lower limb artery perforation	10075730
Lymph node haemorrhage	10074270
Mallory-Weiss syndrome	10026712
Mediastinal haematoma	10049941
Mediastinal haemorrhage	10056343
Medical device site bruise	10075570
Medical device site haematoma	10075577
Medical device site haemorrhage	10075578
Melaena	10027141
Melaena neonatal	10049777
Meningorrhagia	10052593
Menometrorrhagia	10027295
Menorrhagia	10027313
Mesenteric haematoma	10071557
Mesenteric haemorrhage	10060717
Metrorrhagia	10027514
Mouth haemorrhage	10028024
Mucocutaneous haemorrhage	10076048
Mucosal haemorrhage	10061298
Muscle contusion	10070757
Muscle haemorrhage	10028309
Myocardial haemorrhage	10048849

Myocardial rupture	10028604
Naevus haemorrhage	10062955
Nail bed bleeding	10048891
Nasal septum haematoma	10075027
Neonatal gastrointestinal haemorrhage	10074159
Nephritis haemorrhagic	10029132
Nipple exudate bloody	10029418
Ocular retrobulbar haemorrhage	10057571
Oesophageal haemorrhage	10030172
Oesophageal intramural haematoma	10077486
Oesophageal ulcer haemorrhage	10030202
Oesophageal varices haemorrhage	10030210
Oesophagitis haemorrhagic	10030219
Optic disc haemorrhage	10030919
Optic nerve sheath haemorrhage	10030941
Oral blood blister	10076590
Oral confusion	10078170
Oral mucosa haematoma	10074779
Oral purpura	10083533
Orbital haematoma	10083565
Orbital haemorrhage	10031045
Osteorrhagia	10051937
Ovarian haematoma	10033263
Ovarian haemorrhage	10065741
Palpable purpura	10056872
Pancreatic haemorrhage	10033625
Pancreatic pseudocyst haemorrhage	10083813
Pancreatitis haemorrhagic	10033650
Papillary muscle haemorrhage	10059164
Paranasal sinus haematoma	10069702
Paranasal sinus haemorrhage	10080108
Parathyroid haemorrhage	10059051
Parotid gland haemorrhage	10051166
Pelvic haematoma	10054974
Pelvic haematoma obstetric	10034248
Pelvic haemorrhage	10063678
Penile contusion	10073352
Penile haematoma	10070656
Penile haemorrhage	10034305
Peptic ulcer haemorrhage	10034344
Pericardial haemorrhage	10034476
Perineal haematoma	10034520
Periorbital haematoma	10034544
Periorbital haemorrhage	10071697
Periosteal haematoma	10077341
Peripartum haemorrhage	10072693
Peripheral artery aneurysm rupture	10079908

Peripheral artery haematoma	10081077
Peritoneal haematoma	10058095
Periventricular haemorrhage neonatal	10076706
Petechiae	10034754
Pharyngeal contusion	10083176
Pharyngeal haematoma	10068121
Pharyngeal haemorrhage	10034827
Pituitary apoplexy	10056447
Pituitary haemorrhage	10049760
Placenta praevia haemorrhage	10035121
Polymenorrhagia	10064050
Post abortion haemorrhage	10036246
Post procedural contusion	10073353
Post procedural haematoma	10063188
Post procedural haematuria	10066225
Post procedural haemorrhage	10051077
Post transfusion purpura	10072265
Postmenopausal haemorrhage	10055870
Postpartum haemorrhage	10036417
Post-traumatic punctate intraepidermal haemorrhage	10071639
Premature separation of placenta	10036608
Procedural haemorrhage	10071229
Proctitis haemorrhagic	10036778
Prostatic haemorrhage	10036960
Pulmonary alveolar haemorrhage	10037313
Pulmonary contusion	10037370
Pulmonary haematoma	10054991
Pulmonary haemorrhage	10037394
Pulmonary haemorrhage neonatal	10082194
Puncture site bruise	10082035
Puncture site haematoma	10081957
Puncture site haemorrhage	10051101
Purpura	10037549
Purpura fulminans	10037556
Purpura neonatal	10037557
Purpura non-thrombocytopenic	10057739
Purpura senile	10037560
Putamen haemorrhage	10058940
Radiation associated haemorrhage	10072281
Rectal haemorrhage	10038063
Rectal ulcer haemorrhage	10038081
Renal artery perforation	10075737
Renal cyst haemorrhage	10059846
Renal haematoma	10038459
Renal haemorrhage	10038460
Respiratory tract haemorrhage	10038727
Respiratory tract haemorrhage neonatal	10038728

Retinal aneurysm rupture	10079121
Retinal haemorrhage	10038867
Retinopathy haemorrhagic	10051447
Retroperitoneal haematoma	10058360
Retroperitoneal haemorrhage	10038980
Retroplacental haematoma	10054798
Ruptured cerebral aneurysm	10039330
Scleral haemorrhage	10050508
Scrotal haematocoele	10061517
Scrotal haematoma	10039749
Scrotal haemorrhage	10061361
Shock haemorrhagic	10049771
Skin haemorrhage	10064265
Skin neoplasm bleeding	10060712
Skin ulcer haemorrhage	10050377
Small intestinal haemorrhage	10052535
Small intestinal ulcer haemorrhage	10061550
Soft tissue haemorrhage	10051297
Spermatic cord haemorrhage	10065742
Spinal cord haematoma	10076051
Spinal cord haemorrhage	10048992
Spinal epidural haematoma	10050162
Spinal epidural haemorrhage	10049236
Spinal subarachnoid haemorrhage	10073564
Spinal subdural haematoma	10050164
Spinal subdural haemorrhage	10073563
Spleen contusion	10073533
Splenic artery perforation	10075738
Splenic haematoma	10041646
Splenic haemorrhage	10041647
Splenic varices haemorrhage	10068662
Splinter haemorrhages	10041663
Spontaneous haematoma	10065304
Spontaneous haemorrhage	10074557
Stoma site haemorrhage	10074508
Stomatitis haemorrhagic	10042132
Subarachnoid haematoma	10076701
Subarachnoid haemorrhage	10042316
Subarachnoid haemorrhage neonatal	10042317
Subcapsular hepatic haematoma	10083383
Subcapsular renal haematoma	10083385
Subcapsular splenic haematoma	10083384
Subchorionic haematoma	10072596
Subchorionic haemorrhage	10071010
Subclavian artery perforation	10075740
Subclavian vein perforation	10075743
Subcutaneous haematoma	10042345

CCI

Subdural haematoma	10042361
Subdural haematoma evacuation	10042363
Subdural haemorrhage	10042364
Subdural haemorrhage neonatal	10042365
Subendocardial haemorrhage	10082459
Subgaleal haematoma	10069510
Subgaleal haemorrhage	10080900
Subretinal haematoma	10071935
Superior vena cava perforation	10075741
Testicular haemorrhage	10051877
Thalamus haemorrhage	10058939
Third stage postpartum haemorrhage	10043449
Thoracic haemorrhage	10062744
Thrombocytopenic purpura	10043561
Thrombotic thrombocytopenic purpura	10043648
Thyroid haemorrhage	10064224
Tongue haematoma	10043959
Tongue haemorrhage	10049870
Tonsillar haemorrhage	10057450
Tooth pulp haemorrhage	10072228
Tooth socket haemorrhage	10064946
Tracheal haemorrhage	10062543
Traumatic haematoma	10044522
Traumatic haemorrhage	10053476
Traumatic haemothorax	10074487
Traumatic intracranial haematoma	10079013
Traumatic intracranial haemorrhage	10061387
Tumour haemorrhage	10049750
Ulcer haemorrhage	10061577
Umbilical cord haemorrhage	10064534
Umbilical haematoma	10068712
Umbilical haemorrhage	10045455
Upper gastrointestinal haemorrhage	10046274
Ureteric haemorrhage	10065743
Urethral haemorrhage	10049710
Urinary bladder haematoma	10083358
Urinary bladder haemorrhage	10046528
Urogenital haemorrhage	10050058
Uterine haematoma	10063875
Uterine haemorrhage	10046788
Vaccination site bruising	10069484
Vaccination site haematoma	10069472
Vaccination site haemorrhage	10069475
Vaginal haematoma	10046909
Vaginal haemorrhage	10046910
Varicose vein ruptured	10046999
Vascular access site bruising	10077767

	Vascular access site haematoma	10077647
	Vascular access site haemorrhage	10077643
	Vascular access site rupture	10077652
	Vascular anastomotic haemorrhage	10084092
	Vascular graft haemorrhage	10077721
	Vascular pseudoaneurysm ruptured	10053949
	Vascular purpura	10047097
	Vascular rupture	10053649
	Vein rupture	10077110
	Venous haemorrhage	10065441
	Venous perforation	10075733
	Ventricle rupture	10047279
	Vertebral artery perforation	10075735
	Vessel puncture site bruise	10063881
	Vessel puncture site haematoma	10065902
	Vessel puncture site haemorrhage	10054092
	Vitreous haematoma	10071936
	Vitreous haemorrhage	10047655
	Vulval haematoma	10047756
	Vulval haematoma evacuation	10047757
	Vulval haemorrhage	10063816
	Withdrawal bleed	10047998
	Wound haematoma	10071504
	Wound haemorrhage	10051373
Cholestasis and jaundice of hepatic origin	Bilirubin excretion disorder	10061009
	Cholaemia	10048611
	Cholestasis	10008635
	Cholestatic liver injury	10067969
	Cholestatic pruritus	10064190
	Drug-induced liver injury	10072268
	Hepatitis cholestatic	10019754
	Hyperbilirubinaemia	10020578
	Icterus index increased	10021209
	Jaundice	10023126
	Jaundice cholestatic	10023129
	Jaundice hepatocellular	10023136
	Mixed liver injury	10066758
	Ocular icterus	10058117
	Parenteral nutrition associated liver disease	10074151
Hepatic failure, fibrosis and cirrhosis and other liver damage-related conditions	Acquired hepatocerebral degeneration	10080860
	Acute hepatic failure	10000804
	Acute on chronic liver failure	10077305
	Acute yellow liver atrophy	10070815
	Ascites	10003445
	Asterixis	10003547
	Bacterascites	10068547
	Biliary cirrhosis	10004659

CCI

Biliary fibrosis	10004664
Cardiohepatic syndrome	10082480
Cholestatic liver injury	10067969
Chronic hepatic failure	10057573
Coma hepatic	10010075
Cryptogenic cirrhosis	10063075
Diabetic hepatopathy	10071265
Drug-induced liver injury	10072268
Duodenal varices	10051010
Gallbladder varices	10072319
Gastric variceal injection	10076237
Gastric variceal ligation	10076238
Gastric varices	10051012
Gastric varices haemorrhage	10057572
Gastrooesophageal variceal haemorrhage prophylaxis	10066597
Hepatectomy	10061997
Hepatic atrophy	10019637
Hepatic calcification	10065274
Hepatic cirrhosis	10019641
Hepatic encephalopathy	10019660
Hepatic encephalopathy prophylaxis	10066599
Hepatic failure	10019663
Hepatic fibrosis	10019668
Hepatic hydrothorax	10067365
Hepatic infiltration eosinophilic	10064668
Hepatic lesion	10061998
Hepatic necrosis	10019692
Hepatic steato-fibrosis	10077215
Hepatic steatosis	10019708
Hepatitis fulminant	10019772
Hepatobiliary disease	10062000
Hepatocellular foamy cell syndrome	10053244
Hepatocellular injury	10019837
Hepatopulmonary syndrome	10052274
Hepatorenal failure	10019845
Hepatorenal syndrome	10019846
Hepatotoxicity	10019851
Immune-mediated cholangitis	10083406
Immune-mediated hepatic disorder	10083521
Intestinal varices	10071502
Intestinal varices haemorrhage	10078058
Liver dialysis	10076640
Liver disorder	10024670
Liver injury	10067125
Liver operation	10062040
Liver transplant	10024714
Lupoid hepatic cirrhosis	10025129

	Minimal hepatic encephalopathy	10076204
	Mixed liver injury	10066758
	Nodular regenerative hyperplasia	10051081
	Nonalcoholic fatty liver disease	10082249
	Non-alcoholic steatohepatitis	10053219
	Non-cirrhotic portal hypertension	10077259
	Oedema due to hepatic disease	10049631
	Oesophageal varices haemorrhage	10030210
	Peripancreatic varices	10073215
	Portal fibrosis	10074726
	Portal hypertension	10036200
	Portal hypertensive colopathy	10079446
	Portal hypertensive enteropathy	10068923
	Portal hypertensive gastropathy	10050897
	Portal vein cavernous transformation	10073979
	Portal vein dilatation	10073209
	Portopulmonary hypertension	10067281
	Primary biliary cholangitis	10080429
	Regenerative siderotic hepatic nodule	10080679
	Renal and liver transplant	10052279
	Retrograde portal vein flow	10067338
	Reye's syndrome	10039012
	Reynold's syndrome	10070953
	Splenic varices	10067823
	Splenic varices haemorrhage	10068662
	Steatohepatitis	10076331
